#### **5.4 LT-OLE (VISITS 17 TO STUDY CLOSURE)**

Following completion of the first year of LT-OLE the following assessments will be conducted every three months on day 4 (-1) post-dose for all patients:

- Auxology measurements: Actual height (average of 3 consecutive measurements) measured on a calibrated wall mounted stadiometer.
- Overall health status assessment, including complete physical examination and vital signs assessment.
- Individual dose adjustment based on weight.

Effective Date: Date of final electronic approval

- AEs, local tolerability, and concomitant medications.
- Urine pregnancy test at every visit once a female reports first menstrual cycle (menarche).
- Fundoscopy (if there are signs or symptoms indicative of benign intracranial hypertension).
- Return of used and unused injection devices to the site and diary card.
- Drug dispensing and accountability.

The following assessments will also be conducted every six months on day 4 (-1) post-dose visits:

- Assessment of biochemical markers: IGF-1, IGF-1 SDS, IGFBP-3 and IGFBP-3 SDS serum levels.
- Safety laboratory tests: chemistry, hematology and urinalysis.
- Assessment of thyroid function: TSH, FT4.
- Parameters of glucose metabolism: overnight fasting glucose, overnight fasting insulin, HbA1c.
- Parameters of lipid metabolism: overnight fasting cholesterol, triglycerides, HDL, LDL, Lp(a), FFA.
- Assessment of MOD-4023 serum levels.
- Assessment of anti-MOD-4023 Ab.

Additional assessments will be performed once a year, every 12 months on dosing day or Day 4(-1):

- ECG.
- Bone age.
- Pubertal status (according to Tanner stages).
- For males that are 13 years and older: LH, FSH and testosterone. For females that are 12 years and older: LH, FSH and estradiol.

The following assessments will be conducted during the EOS/ET visit:

- Auxology measurements- Actual Ht (mean of 3 consecutive measurements) measured on a calibrated wall mounted stadiometer.
- AEs, local tolerability, and concomitant medications.
- Overall health status assessment, including complete physical examination and vital sign assessments.
- Safety laboratory (chemistry, hematology and urinalysis).
- Pubertal status.
- Urine pregnancy test for female patients who have reported menarche.
- Thyroid function and biochemical markers: TSH, FT4, IGF-1, IGF-1 SDS, IGFBP-3 and IGFBP-3 SDS serum levels.
- Parameters of glucose metabolism (overnight fasting glucose, overnight fasting insulin, HbA1c).

Effective Date: Date of final electronic approval

- Parameters of lipid metabolism (overnight fasting cholesterol, triglycerides, HDL, LDL, Lp(a), FFA).
- For males that are 13 years and older: LH, FSH and testosterone. For females that are 12 years and older: LH, FSH and estradiol.
- Fundoscopy (ONLY if there are signs or symptoms indicative of increased intracranial hypertension).
- Bone age.
- MOD-4023 serum levels.
- ECG.
- Return of used and unused injection devices and diary cards.
- Anti-MOD-4023 Abs.

Patients will be required to visit the study site for assessment of biochemical markers on day 4 (-1) post-dose. If a visit is performed on a dosing day, collection of MOD-4023 serum levels and anti-Mod-4023 Ab levels must be obtained pre-dose. For End of Treatment during LT-OLE Year 1, the ECG will be conducted at 7-12 hours post-dose and patients will be requested to inject MOD-4023 during the day/night at their convenience and come to the study site at the requested timepoint for the ECG. An ECG must still be obtained even if patients do not take the final dose. Visits may be split to allow for pre-dose blood collection for serum levels and antibody tests and post-dose ECG or the patient will be asked to come to the study site for blood collection, administer the required dose, and return to the study site 7-12 hours post-dose. For ET from LT-OLE Year 2 onwards ECG can be conducted without a timeframe requirement i.e. at any time, although the date and time that each is performed will be recorded.

Patients will be contacted by telephone 30 days [ $\pm$  5 days] after EOS/ET visit in order to obtain safety related information.

### 5.5 EARLY DISCONTINUATION STUDY VISIT

If, during the main study, a patient discontinues prematurely from the study for the reasons specified in Section 4.4, the same procedures planned for Visit 8 (12 months/Wk 52 [ $\pm$ 1 wk]) will be conducted. Other procedures and evaluations will be completed as deemed necessary by the Investigator.

If, during the LT-OLE, a patient discontinues prematurely from the study for the reasons specified in Section 4.4, the same procedures for LT-OLE EOS/ET will be conducted.

### 5.6 UNSCHEDULED VISIT

An unscheduled visit may be performed at any time during the study at the patient's request or as deemed necessary by the Investigator or requested by the Global Study MM. The date and reason for the unscheduled visit will be recorded. AE monitoring and concomitant medication recording will be performed by the Investigator. Other procedures and evaluations will be completed as deemed necessary by the Investigator and may include (but not limited to) laboratory tests, ECG, vital signs and physical examination.

## 5.7 EFFICACY ASSESSMENTS AND ENDPOINTS

### 5.7.1 Ht and Annual HV

Ht measurements must be performed according to [Appendix C](#) with a calibrated wall-mounted (e.g. Harpenden or similar) stadiometer and should ideally be conducted at the same time of the day for each visit, preferably in the morning. To ensure consistency of results, ideally the same auxologist will perform these measurements for each patient at each visit to minimize the variability of measurements. The time of measurement and the observer's initials is to be recorded in the eCRF. Three (3) independent readings will be recorded for each visit in the eCRF.

The Ht Standard Deviation Score (Ht SDS) will be derived from the age and gender standards from 2000 Center for Disease Control Growth Charts ([www.cdc.gov/growthcharts](http://www.cdc.gov/growthcharts)) by the Sponsor during the study.

Annualized HV will be calculated in cm as the change in Ht from Visit 2 to Visit 8 (after 12 months of treatment) during the main study and again every 12 months thereafter compared to the measurement taken 12 months prior during the LT-OLE.

### 5.7.2 BA

BA will be determined by X-ray according to Greulich-Pyle method ([Greulich 1959](#)) using central BA reader during the main study at Screening (Visit 1), Visit 2a, and Visit 8 (Month 12). X-ray films of the left hand and wrist will be taken as outlined in [Appendix D](#) and will be sent to a qualified central reader. The central reader will be blinded to the CA, drug allocation, and name of the patients. X-ray films will hold only an identification number and gender. Details of the central BA reader and the procedure for blinding and shipping of X-rays will be provided to the investigator.

During the LT-OLE, BA will be determined by X-ray every 12 months. The central reader will be blinded to the CA and name of the patient.

### 5.7.3 Biochemical Markers: IGF-1 and IGFBP-3

hGH stimulates hepatic production and release of IGF-1 into the systemic circulation. IGF actions are modulated by a family of 6 structurally-related binding proteins (IGFBPs 1-6), which bind IGFs, but not insulin with high affinity. More than 99% of IGFs bind to IGFBPs. In particular, IGFBP-3 is the predominant circulating IGFBP.

Clinical evaluations of IGF-1, IGF-1 SDS, IGFBP-3 and IGFBP-3 SDS will be performed at every study visit during the main study except Visits 3, 6a, 6b, 8a, and 9. During the LT-OLE, these evaluations will be performed as per the schedule of events in [Appendix A](#).

## 5.8 SAFETY ASSESSMENTS AND ENDPOINTS

Safety assessments will be based on changes from baseline of clinical AEs (including local tolerability, i.e. injection site reaction) reported by the patient or observed by the investigator, concomitant medication use, treatment compliance, vital signs, ECG, physical examination, fundoscopy and laboratory assessments (hematology, blood chemistry, glucose metabolism, lipid

a If not done with the central reader during the Screening visit.

metabolism, thyroid function, IGF-1 levels, immunogenicity and urinalysis). AEs and concomitant medication use will be assessed at every visit. Physical examination and safety laboratory assessments will be performed according to the schedule of events in Appendix A.

#### 5.8.1 AEs

AEs, including local tolerability (i.e. injection site reactions), will be assessed at all study visits (excluding Visits 1 and 6b) throughout the study. In addition, patients will be requested to complete a patient diary at home to collect data on AE, concomitant medications and local tolerability.

Any AEs that occur throughout the study will be recorded. Any new AE that occurs between scheduled visits should be brought to the attention of the investigator and recorded in the patient's medical file and on the appropriate eCRF page. AEs should be followed until resolution or stabilization.

#### 5.8.2 Local Tolerability (Injection Site Reactions)

Assessment of local tolerability will be performed by examining the injection sites (by the investigator if a reaction is present at the time of every visit, excluding Visit 1) and on the basis of anamnestic data and records in the patient diary. Observations of local injection site reactions will be recorded on the appropriate eCRF pages.

The patients and parents/legal guardians will be trained to record, at least once weekly, any injection site reaction in their diaries.

An abnormal injection site reaction is defined as:

- Injection site reaction which is reported or observed at the time of visit or during a phone call and is of moderate to severe in intensity.
- Injection site reaction between the last and present visit or remaining at the time of visit which require medical attention, or injection site reaction resulting from a previous injection, other than the last injection.
- Any other injection site reaction deemed abnormal to the investigator's judgment, other than those ordinarily observed in subcutaneous injections.
- Pain score  $\geq 4$  (as reported in the patient diary).

If an injection site reaction meets the criteria for "abnormal" defined above, it will be considered and assessed as an AE.

- Pain: For patients, injection site pain will be evaluated by the investigator or designated personnel if the injection is given at the medical center, and by the parent/legal guardian if the injection is given at home. The pain will be evaluated at least once weekly using a Pain Rating Scale and recorded in the patient diary. In addition, each patient and parent/guardian will be queried during study visits regarding possible injection site pain.
- Pain score  $\geq 4$  should be reported as an AE.

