## 5.2 MAIN STUDY TREATMENT PERIOD (DAY 1/BASELINE TO MONTH 12)

Eligible patients will be randomized (central randomization within each regiona) in a 1:1 fashion within each stratum to receive either weekly MOD-4023 (0.66 mg/kg/wk) or daily Genotropin® (0.034 mg/kg/day or 0.24 mg/kg/wk) for 12 months.

Visit 2 (Day 1/Baseline) will be conducted on day of first dosing. Subsequent visits, Visit 4 (Month 1/Wk 4 [+1 wk]), Visit 5 (Month 3/Wk 13 [ $\pm 1$  wk]), Visit 6 (Month 6/Wk 26 [ $\pm 1$  wk]), Visit 7 (Month 9/Wk 39 [ $\pm 1$  wk]), and Visit 8 (Month 12/Wk 52 [ $\pm 1$  wk]) will be conducted on day 4 (-1 day) post doseb to obtain IGF-1 measurements expected to reflect average levels throughout the wk.

Visit 3 (Day 10 [+4 days]c post first dose) for the collection of immunogenicity and PK sample will be conducted for MOD-4023 arm only. This visit can be done at the patient's home or at the study site, based on local regulations and nurse availability. If home visit is conducted, a questionnaire, as described in [Appendix I](#) should be completed, collecting information on AE, local tolerability and concomitant medications.

Visits 6a (Month 6/Wk 26 [ $\pm 3$  wk]) and Visit 8a (Month 12/Wk 52 [ $\pm 1$  wk]) will be conducted on dosing day for the MOD-4023 arm only for the collection of immunogenicity and PK sample. This visit can be done at the patient's home or at the study site, based on local regulations and nurse availability. If home visit is conducted, a questionnaire as described in [Appendix I](#) should be completed as well. Samples must be collected prior to dosing of MOD-4023.

In parallel to MOD-4023 patients Visit 3 (Day 10 [+4 days]), a phone interview will be conducted to Genotropin® arm patients and/or parents/guardians according to the questionnaire provided in [Appendix I](#) in which AE, local tolerability and concomitant medication information will be collected.

For the ECG that will be conducted at Visit 6b (Month 6/Wk 26 [ $\pm 3$  wks]) at 7-12 hours post-dose for MOD-4023 treated patients, patients will be requested to inject MOD-4023 during the day/night at their convenience and come to the study site at the requested time point for ECG.

Visits 6a and 6b might be combined on the same day (only if 6a is done prior to dosing).

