### 5.2.5 Visit 5 (Month 3/Wk 13 [ $\pm 1$ wk]), Visit 6 (Month 6/Wk 26 [ $\pm 1$ wk]), Visit 7 (Month 9/Wk 39 [ $\pm 1$ wk]), Visit 8 (Month 12/Wk 52 [ $\pm 1$ wk])

The following assessments will be conducted at Visits 5, 6, 7 and 8 on Day 4 (-1) post dose:

- Auxology measurements: Actual Ht (mean of three consecutive measurements) measured on a calibrated wall mounted stadiometer.
- AEs, local tolerability, and concomitant medications.
- Overall health status assessment, including complete physical examination and vital signs.
- Safety laboratory tests: chemistry, hematology and urinalysis.
- Pubertal status (according to Tanner stages);
- Urine pregnancy test at every visit once a female patient reports first menstrual cycle (menarche).
- Assessment of thyroid function and biochemical markers: TSH, FT4, IGF-1, IGF-1 SDS, IGFBP-3 and IGFBP-3 SDS serum levels.
- Parameters of glucose metabolism: overnight fasting glucose, overnight fasting insulin, HbA1c.
- Parameters of lipid metabolism: overnight fasting cholesterol, triglycerides, HDL, LDL, Lp(a), FFA.

a For the Genotropin® arm a visit by phone interview will be conducted as described in [Appendix I](#).

- Fundoscopy (ONLY if there are signs or symptoms indicative of increased intracranial hypertension).
- BA at Visit 8 only.
- Individual dose adjustment every three months.
- Drug dispensing and accountability.
- MOD-4023 serum levels (MOD 4023 patients only).
- Anti-hGH Ab (Genotropin® patients only).
- ECG (Visit 6 only for Genotropin® patients). Patients in the Genotropin® arm will be requested to inject the study drug preferably at night and come to the clinic the following day for ECG assessment.
- Return of used and unused injection devices and diary cards.
- Return of completed PAT forms (USA only) (Visit 5 only) (applicable for MOD-4023 arm only).
- Anti-MOD-4023 Ab (Visits 5 and 7, MOD-4023 arm only, Visit 8 both arms).
- Informed consent for the LT-OLE (Visit 7 (preferred) or 8).
- QoL questionnaire (QoLISSY) at Visit 8 only.
- For males that are 13 years and older: LH, FSH and testosterone. For females that are 12 years and older: LH, FSH and estradiol (Visit 8 only).

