### 6.3 STUDY DRUG ADMINISTRATION

MOD-4023 will be administered as a SC injection preferably (but not required) in the morning hours once weekly, using the PEN into the upper arms, buttocks, thighs, or abdomen (8 locations). It is recommended that all 8 injection sites are used successively, using a different injection site at each subsequent injection. The same injection site should be used only after all other injection sites have been rotated (see recommended rotation scheme below).

The starting dose for the administration will be 0.66 mg/kg/wk. All patients on Genotropin® that complete Visit 8/10 and continue into the LT-OLE will start treatment with MOD-4023 at 0.66 mg/kg/wk.

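### The injection-site AE criterion in Protocol Section 5.8.2 counts injections rather than time, so the case definition differs between daily Genotropin and weekly MOD-4023

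*Protocol*

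**What the plan says.** Protocol Section 5.8.2 lists the ways in which an injection-site reaction becomes abnormal. One is that it "is of moderate to severe in intensity". Others are a need for medical attention, a diary pain score of 4 or more, and investigator judgment ("Any other injection site reaction deemed abnormal to the" investigator, beyond what is ordinarily seen after subcutaneous injections). A further route is an "injection site reaction resulting from a previous injection, other than the last injection". Any reaction that meets one of these "it will be considered and assessed as an AE". Appendix H refers back to the same definition.

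Section 5.2 randomizes patients "to receive either weekly MOD-4023 (0.66 mg/kg/wk) or daily Genotropin". Section 6.3 confirms the weekly schedule and Section 6.2 the daily one. Visit timing is tied to the weekly dose: "The following assessments will be conducted at Visits 5, 6, 7 and 8 on Day 4 (-1) post dose" (Section 5.2.5), and Section 5.2.4 sets the same day for Visit 4.

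AE incidence and local injection-site reaction assessment are separate safety endpoints (Section 8.4.4). Section 8.6.6 rests the safety assessment mainly on the frequency of treatment-emergent AEs, and Section 8.6.7 tabulates AEs by treatment group.

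**The concern.** A case definition used to compare two arms should give the same answer for the same clinical finding. This clause asks whether another injection has been given since the one that caused the reaction, and the answer depends on the dosing schedule. The identical mild redness can be an AE in one arm and not in the other. Tolerability of the weekly product is a secondary objective, and AE frequency by arm is the main safety display. A difference in injection-site AE incidence could therefore come partly from the definition and be read as a difference between products.

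**Working it through.** The plan states no figure on this point, so there is nothing to reproduce. The check is one of logic, with one small calculation for an alternative reading.

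**Inputs**
- Dosing interval T: 1 day on Genotropin (Section 6.2), 7 days on MOD-4023 (Section 6.3).
- Limits in the clause: none on severity or duration (Section 5.8.2).
- Visits 4 to 8: 3 or 4 days after the weekly dose (Sections 5.2, 5.2.4, 5.2.5).
- Assumption: doses are given on schedule, one injection per dose.

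**Step 1: when the clause is met.** A reaction aged a days comes from an injection other than the last if at least one later injection has been given, that is, if a ≥ T.

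| Age of reaction | Genotropin (T = 1) | MOD-4023 (T = 7) |
|---|---|---|
| 0 days | no | no |
| 1 to 6 days | yes | no |
| 7 days or more | yes | yes |

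The arms disagree for every age from 1 to 6 days.

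**Step 2: at a scheduled visit.** Take a mild reaction aged 3 days. On MOD-4023, 3 < 7, so it still belongs to the last injection and the clause is not met. On Genotropin, 3 ≥ 1, about three later injections have followed, and the clause is met.

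**Step 3: do the other criteria even this out?** The severity criterion does not reach a mild reaction. Medical attention and a pain score of 4 or more do not apply to a mild reaction without those features. Investigator judgment sets aside what is ordinary after subcutaneous injection. These criteria are the same in both arms and leave the difference in Step 1 in place.

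**Step 4: the wider reading.** The bullet that contains the clause opens with reactions occurring between visits, so the clause might also cover resolved reactions reported in the diary. Then only the most recent injection before a visit is exempt. Over a 13-week visit interval:
- MOD-4023: 13 injections, exempt share 1/13 = 7.7%, covered 92.3%.
- Genotropin: 13 × 7 = 91 injections, exempt share 1/91 = 1.1%, covered 98.9%.
- Difference in coverage: 98.9 − 92.3 = 6.6 percentage points.

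The gap is much smaller but runs the same way, and the visit example in Step 2 is unchanged.

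**The case against.** The strongest reply is that this clause is only one part of ascertainment, and other parts run the opposite way. The synopsis has MOD-4023 patients complete a diary after every injection and Genotropin patients once a week, about one entry per seven injections, and the pain criterion draws on that diary. The MOD-4023 arm has additional visits with a tolerability assessment (6a and 8a in Section 5.2.6, and 6b in Appendix A). Its Visit 3 is in person, while the Genotropin arm has a telephone interview. A reader might infer that the tolerability comparison is biased in favour of MOD-4023. The documents do not support that: they give no way to weigh these opposing effects. What stands is narrower. More frequent capture does not make the definition equal, and the direction of this clause alone is clear.

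It can also be said that safety reporting is descriptive, so no formal error rate is affected. Every observed reaction goes on eCRF pages, and local reaction assessment is already a separate endpoint to be tabulated (Section 8.6.6). All of this is correct and limits the consequence. It does not mend the AE tables. Section 8.5 foresees two SAPs and the one supplied covers only the LT-OLE, so how the main-study local reactions will be displayed cannot be judged.

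Two details soften the contrast. An investigator may still call a mild MOD-4023 reaction abnormal. When a MOD-4023 dose is split (Section 6.3), the first of the two injections is literally not the last.

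**Conclusion.** The point holds as a flaw in the definition. Injection-site AEs have an arm-dependent case definition, with a duration threshold of about 1 day on Genotropin and about 7 days on MOD-4023 for mild reactions still present. Taken alone, the clause inflates injection-site AEs on Genotropin relative to MOD-4023. This rests on on-schedule dosing and on reading the clause literally; under the wider reading the gap shrinks to the coverage difference in Step 4.

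Two further inferences are tempting and should not be drawn. A reader might turn the two thresholds into percentages of reactions by assuming a distribution of durations. The documents give no durations, and such a share would describe reactions that outlast the next injection, not those seen, reported and coded. A reader might also infer a distorted before-and-after comparison in children who switch to MOD-4023 in the LT-OLE. The SAP assigns AEs to study periods (Appendix 2.1) but plans no such contrast.

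**What to change.** In Section 5.8.2, replace the injection-count wording with one elapsed-time criterion that is the same in both arms: a reaction still present more than a fixed number of hours after the injection that caused it. The sponsor sets the number. Appendix H follows, since it refers back to this definition.

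For data already collected:
- Name the graded eCRF local-reaction records, regardless of AE status, as the basis of the between-arm tolerability comparison. This is already a listed safety endpoint, so it needs little beyond what is planned. State beside the table that diary and visit frequency differ by arm.
- Show injection-site AE incidence by arm with and without mild events. Section 7.1 records AE severity, so this is feasible. Isolating events that qualified only through this clause may not be, because the AE form contents listed there include no field for the qualifying criterion. Dropping all mild events also removes those that qualified by another route, which is why both versions are needed.

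The cost is one sentence in the protocol and a small addition to the tables. The downside is that AE counts before and after the wording change are not strictly comparable; the graded records do not depend on that wording.
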